13.6.6. Prior and Concomitant Medications

Medications will be recorded at each study visit during the study and will be coded using World Health Organization-Drug dictionary (WHO-DD) September 2015, or later.

All medications and supplements taken within 60 days prior to informed consent through the duration of the study will be recorded, as well as all medications used to treat PD regardless of timing. Those medications taken prior to the first dose of IP will be denoted “Prior”. Those medications taken prior to the first dose of IP and continuing beyond the initiation of the IP or those medications started at the same time or after the initiation of the IP will be denoted “Concomitant”.

Medications will be presented according to whether they are “Prior” or “Concomitant” as defined above. If medication dates are incomplete and it is not clear whether the medication was concomitant, it will be assumed to be concomitant.

Details of prior and concomitant medications will be listed by participant, start date, and verbatim term.

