16.1 Adverse Events

TEAEs are defined as any AEs with an onset date on or after the date of the first dose of IP or any worsening of a preexisting medical condition/AE with onset after the start of IP and throughout the study. An AE leading to treatment discontinuation is defined as an AE with action taken of investigational product as Drug Withdrawn. AEs will be coded using the Medical Dictionary for Regulatory Activities MedDRA version 23.0u.

An overall summary of TEAEs, including the number of events, reported, the number and percentage of participants reporting at least one TEAE, the number and percentage of participants reporting at least one related TEAE, the number and percentage of participants by maximum severity, the number and percentage of participants discontinuing due to an adverse event, the number and percentage of participants with at least one serious adverse event, and the number and percentage of deaths will be presented.

A breakdown of the number and percentage of participants reporting each adverse event, categorized by System Organ Class (SOC) and preferred term (PT), will be presented. Note that counting will be by participant, not event, and participants are only counted once within each SOC and PT.

A further tabulation of these data, categorized by relationship (to SAGE-718), will be presented. Participants with multiple events within a particular body system or preferred term will be counted under the category of their drug-related event (related and not related) within SOC and PT. Relationship to SAGE-718 is categorized as related or not related.

A summary of events reported, categorized by severity, will also be provided. Participants with multiple events within a particular SOC and PT will be counted under the category of their most severe event in the following order: severe > moderate > mild within that SOC and PT.

A summary of adverse events leading to discontinuation of SAGE-718 will be provided, grouped by body system and preferred term.

All adverse events (including non-treatment-emergent events) recorded on the CRF will be listed.

Handling of missing AE start dates is defined in Appendix 3. Missing data for severity or relatedness to treatment will not be imputed.

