19.4 Appendix-D Adverse Event Start/Stop Date Imputation

[figure not shown]
Parameter	Missing	Additional Conditions	Imputation
Start date for AEs	D	M and Y same as M and Y of investigational product administration	Date of investigational product administration
		M and/or Y not same as date investigational product administration	First day of month
	D and M	Y same as Y of investigational product administration	Date of investigational product administration
		Y prior to Y of investigational product administration but same as Y of screening date	Date of screening date
	D, M, Y	None - date completely missing	Date of investigational product
Stop date for AEs	D	M and Y same as M and Y of investigational product administration	Date of investigational product administration
		M and/or Y not same as date of investigational product administration	Use last day of month
	D and M	Y same as Y of investigational product administration	Date of investigational product
		Y not same as Y of investigational product administration	Use Dec 31
	D, M, Y	None - date completely missing	No imputation, but assume ongoing

[figure not shown]
Note: In all cases, if an estimated start date is after a complete stop date, use the first day of the stop date month. Similarly, if the estimated stop date is before a complete or imputed start date, use the last day of the start day month.

[figure not shown]

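### A TEAE with no relatedness or severity rating has no place in the related and severe counts, so those percentages are lower bounds; overall TEAE incidence is unaffected

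*SAP*

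**What the plan says.** On unrated events, SAP 16.1 says only: "Missing data for severity or relatedness to treatment will not be imputed".

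The tables it describes use closed lists. For causality, "Relationship to SAGE-718 is categorized as related or not related", and the overall summary reports "the number and percentage of participants reporting at least one related TEAE". For severity, participants with several events are "counted under the category of their most severe event in the following order: severe > moderate > mild within that SOC and PT". Neither list has a missing category, and the table titles in SAP Appendix G (14.3.1.1, 14.3.1.7 and 14.3.1.8, each for Parts A and B) do not indicate one.

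Missing AE start dates are handled differently. In SAP Appendix D the date of dosing is used when only the day is missing and "M and Y same as M and Y of investigational product administration", when day and month are missing but the year is the dosing year, and when the condition is "None - date completely missing". SAP 16.1 counts onset on the first-dose date as treatment-emergent, so all three routes put the event in the TEAE total. A completely missing AE stop date gets "No imputation, but assume ongoing". For medications, Protocol 13.6.6 says: "If medication dates are incomplete and it is not clear whether the medication was concomitant, it will be assumed to be concomitant".

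**The concern.** The investigator's classification of an event as not related is a positive judgement (Protocol 12.2.3). An event nobody assessed has had no such judgement, yet it affects the related count exactly as a not-related event does: it adds nothing. Severity works the same way. If a participant has one mild and one ungraded event under the same preferred term, the highest available grade is mild, and mild is what the table shows.

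The effect runs in one direction only. A poorly documented event can be brought into the TEAE total by the start-date rule and then be absent from the related and severe rows. With 11 and 22 planned participants, one blank field is visible in a percentage. At stake is how the relatedness and severity breakdowns read in a study whose primary objective is safety and tolerability.

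**Working it through.** **Inputs**
- Planned participants: N = 11 in Part A and N = 22 in Part B (Protocol 7.2, SAP 10.1). The parts are tabulated separately (SAP 13.1).
- r = participants with at least one TEAE rated related (or severe).
- m = participants not in r who have at least one TEAE with that rating missing. The documents give no value; 0, 1 and 2 are assumed here to show the range.

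**The plan's own figure.** For 10 and 20 completers with 10% dropout, 10 × 1.10 = 11 and 20 × 1.10 = 22, total 33, as stated. Dividing by 0.90 instead gives 11.1, 22.2 and 33.3. The difference is a fraction of a participant and does not matter here.

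**Step 1: bounds.** As written, the table shows r/N. If every missing rating were the unfavourable one, it would show (r + m)/N. Full rating would give a value between the two, so the reported figure is a lower bound and the largest possible shortfall is m/N.

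**Step 2: numbers.** Per affected participant, 1/11 = 9.1 points and 1/22 = 4.5 points. Exact (Clopper-Pearson) 95% intervals are added for scale in the r = 0 rows with m above 0; the plan does not call for them.

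| r | m (assumed) | Part A as written | Part A upper bound | Part B as written | Part B upper bound |
|---|---|---|---|---|---|
| 0 | 0 | 0% | 0% | 0% | 0% |
| 0 | 1 | 0% (0 to 28.5) | 9.1% (0.2 to 41.3) | 0% (0 to 15.4) | 4.5% (0.1 to 22.8) |
| 0 | 2 | 0% (0 to 28.5) | 18.2% (2.3 to 51.8) | 0% (0 to 15.4) | 9.1% (1.1 to 29.2) |
| 1 | 1 | 9.1% | 18.2% | 4.5% | 9.1% |

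A participant who already has another event rated related (or severe) is in r and adds nothing to m.

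**Step 3: primary endpoint.** Overall incidence is the number of participants with any TEAE divided by N. No rating enters it, so m does not change it.

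**Step 4: direction compared with the date rules.** The AE start-date rule, the rule for a completely missing AE stop date and the protocol's concomitant default all settle doubt towards inclusion or continuation. Other date rules do not. A partial AE stop date in the dosing month or year is set to the dosing date, which can shorten the event. A completely missing medication start date is set to the day before dosing (SAP Appendix C). The contrast therefore holds for AE start dates in particular, not for the date rules as a whole.

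**The case against.** The strongest reply is that the sentence applies the plan's stated policy. Protocol 13.2 and SAP 13.1 both say missing data will not be estimated, so there is no textual contradiction. That stands: this is a difference of direction between rules. But SAP 13.1 also refers to date imputation for AEs and medications, so the policy already has exceptions where a classification depends on a missing item.

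Second, missing ratings should be few. Protocol 12.2.3 requires a causality decision for each AE, Protocol 12.2.4 requires intensity and causality, and monitors check AE documentation (Protocol 14.1). This also stands, and it keeps the point minor.

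Third, exclusion of unrated events is an inference from no imputation plus closed category lists. The SAP does not forbid a missing row, and the table shells are not in the documents. All AEs are listed, so a blank rating could be found. That is fair; what remains is that the plan does not say how such an event is tabulated.

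Fourth, grading every ungraded event as severe would create a grade nobody assigned. One blank field could produce a 9.1% severe rate in Part A. This objection is accepted, and the fix does not do that.

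Three stronger readings are tempting but unsupported. A reader might infer that the primary endpoint is understated; it counts TEAEs of any grade and relationship, so it is not. A reader might infer that the plan breaks its own general worst-case policy for dates; Step 4 of the working shows it has none. A reader might infer that blanks would cluster in participants lost early; nothing in the documents says so.

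**Conclusion.** The point holds as a minor gap in the safety tables. Under SAP 16.1 as written, the related and severe percentages are lower bounds whenever a rating is missing, and the plan does not say where an unrated event is shown. The size is up to 9.1 points in Part A or 4.5 points in Part B for one affected participant, and zero if all ratings are complete. These figures assume the planned denominators, one participant not already in the relevant count, and a missing rating that would have been unfavourable. The wide intervals show that a one-participant shift does not by itself change what so small a study can conclude. The case for the change is that it is cheap and removes a one-sided effect.

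**What to change.** Replace the no-imputation sentence in SAP 16.1 with:

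> In summary tables a TEAE with missing relationship is counted as related; a TEAE with missing severity is shown in a separate Missing row, with a footnote giving the severe count if these were counted as severe; listings show the value as missing.

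Because the severity table counts each participant once per term, a programming note should say where a participant with both a graded and an ungraded event in the same term appears; the footnoted count should include such participants.

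Counting missing relatedness as related departs from the general rule in Protocol 13.2, so it should be recorded in SAP 6.1. If the database is already locked, SAP 6.0 requires the change and its justification to be described in the clinical study report.

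The cost is one replaced sentence, one entry in SAP 6.1, and a row or footnote in the overall, relationship and severity tables for each part. No extra data are needed. The downside is that the related percentage may be slightly less favourable if any relationship is missing; if no ratings are missing, no count changes.

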16.1.1 Deaths and Serious Adverse Events (SAEs)

All deaths and SAEs will be listed.

16.2 Clinical Laboratory Evaluations

Laboratory assessments for biochemistry, coagulation, hematology, urinalysis, and serology, will be collected at screening, on Day -1, Day 7, Day 14, and Day 28 for Part A, whereas for Part B it is collected at screening, on Day -1, Day 14, Day 28 and Day 42. The clinical laboratory tests to be performed for monitoring safety are listed in **Table 4**. Laboratory assessments will be summarized (n, mean, std, median, Q1, Q3, minimum, and maximum) for Part A and Part B along with the change from baseline by each scheduled post-baseline visit. The International System of Unit (SI) will be used.

For the laboratory results that is " $< \text{ or } = x$ ", where x is a number as collected in the data, the numeric part of the result will be used in the calculation in the summary tables. The same is true if the result is presented as below limit of quantification (BLQ) and a lower limit of quantification (LLOQ) value is provided – LLOQ value will be used for calculation in the summary tables. The actual results as collected will be displayed in the listings.

Summary tables on lab parameters will include descriptive statistics for the observed values and changes from baseline by scheduled assessment timepoint in hematology, serum chemistry, coagulation, and quantitative urinalysis test results.

Table 4 Clinical Laboratory Tests

Hematology	Serum Chemistry	Urinalysis	Coagulation
Red blood cell count	Alanine aminotransferase	pH	Activated partial
Hemoglobin	Albumin	Protein	Thromboplastin
Hematocrit	Alkaline phosphatase	Glucose	time
White blood cell count with differential	Aspartate aminotransferase	Red blood cell	Prothrombin time
Platelet count	Total bilirubin	Nitrite	International
Red Blood Cell Indices (MCV, MCH, MCHC)	Direct bilirubin	Leukocyte esterase	normalized ratio
Reflex to Red blood cell morphology if indices are abnormal	Indirect bilirubin	Ketones	
	Total protein	Bilirubin	
	Creatinine	Urobilinogen	
	Blood urea nitrogen		
	Creatine kinase		
	Gamma-glutamyl transferase		
	Potassium		
	Sodium		
	Lactate dehydrogenase		
	Glucose		
	Chloride		
	Bicarbonate		
	Calcium		
	Phosphate		
	Triglycerides		
	Thyroid-stimulating hormone (TSH)		

If a normal range is provided for the parameter, out-of-range values will be flagged as low or high, where applicable, in the participant data listings

The number and percentage of participants with potentially clinically significant (PCS) values will be provided in separate displays in hematology, serum chemistry, and liver function tests provided for such occurrence by time point.

PCS values will be identified for specific laboratory parameters as outlined in Table 5.

Liver function tests will be monitored closely for PCS values, and will be summarized for an occurrence at any post-baseline visit for the following parameters for these PCS threshold (for conditions involving more than one parameter, the results need to be from the same timepoint):

Alanine Aminotransferase: >3xULN, >5xULN, >10xULN
 Aspartate Aminotransferase: >3xULN, >5xULN, >10xULN
 Alanine Aminotransferase or Aspartate Aminotransferase: >3xULN, >5xULN, >10xULN
 Alkaline Phosphatase: >1.5xULN, >2xULN
 Total Bilirubin: >1.5xULN, >2xULN
 Total Bilirubin > 2xULN **AND** (Alanine Aminotransferase or Aspartate Aminotransferase >3xULN)
 Total Bilirubin >2xULN **AND** Alkaline Phosphatase >2xULN **AND** (Alanine Aminotransferase or Aspartate Aminotransferase >3xULN)

Any lab results considered clinically significant by the investigator will be captured as adverse events, and hence will show up in AE displays.

Pregnancy test results will be listed.

Table 5 Potentially Clinically Significant Values for Specific Laboratory Parameters

Laboratory Parameter	Gender	Units	Criteria for PCS Values (Observed values)	
			High	Low
Hematology				
Hemoglobin	Male	g/L	>185	<115
	Female	g/L	>170	<100
Hematocrit	Male	Fraction of 1	>0.55	<0.385
	Female	Fraction of 1	>0.49	<0.345
Platelet count		10 ⁹ /L	>600	<125
White blood cell		10 ⁹ /L	>15	<2.5
Basophils		10 ⁹ /L	>0.5	NA
Eosinophils		10 ⁹ /L	>1.5	NA
Neutrophils		10 ⁹ /L	NA	<1.5
Lymphocytes		10 ⁹ /L	>6.0	<0.5
Monocytes		10 ⁹ /L	>1.4	NA

Laboratory Parameter	Gender	Units	Criteria for PCS Values (Observed values)	
			High	Low
Serum Chemistry				
Albumin		g/L	>70	<28
Blood urea nitrogen		mmol/L	>10.71	NA
Calcium		mmol/L	>2.75	<2.0
Chloride		mmol/L	>120	<90
Creatinine		mmol/L	>3xULN or >3x Baseline	
Gamma Glutamyl Transferase			>3xULN	
Glucose		mmol/L	>13.9	<2.8
Sodium		mmol/L	>150	<132
Potassium		mmol/L	>5.4	<3.3
Protein		g/L		<45
Bicarbonate		mmol/L	>34	<18
Phosphorus		mmol/L	>1.94	<0.61
Liver Function Tests (LFT)				
Bilirubin		µmol/L	>2xULN	NA
Aspartate Aminotransferase		U/L	>3xULN	NA
Alanine Aminotransferase		U/L	>3xULN	NA
Alkaline Phosphatase		U/L	>1.5xULN	NA

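### The joint bilirubin and transaminase count in SAP 16.2 omits a participant whose two elevations fall at different visits

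*SAP*

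**What the plan says.** SAP 16.2 gives liver tests their own set of thresholds. They "will be summarized for an occurrence at any post-baseline visit for the following parameters for these PCS threshold", so the counting period is the whole post-baseline phase. A parenthesis in the same sentence then limits the multi-analyte criteria: "for conditions involving more than one parameter, the results need to be from the same timepoint".

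The limit has effect on only two rows, the ones joined by AND:

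- bilirubin with transaminase: "Total Bilirubin > 2xULN AND (Alanine Aminotransferase or Aspartate Aminotransferase >3xULN");
- the same condition with raised alkaline phosphatase (ALP) added: "Total Bilirubin >2xULN AND Alkaline Phosphatase >2xULN AND (Alanine Aminotransferase or Aspartate Aminotransferase >3xULN").

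Each analyte also has rows of its own, for example "Total Bilirubin: >1.5xULN, >2xULN", and there is a row for either transaminase at >3, >5 and >10xULN.

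On sampling, Part A laboratory tests after baseline fall on Days 7, 14 and 28. The SAP states that "for Part B it is collected at screening, on Day -1, Day 14, Day 28 and Day 42". Appendix G, as shown, has a table of potentially clinically significant biochemistry results for each Part and a by-participant biochemistry listing (Listing 16.2.8.2). It shows no separate display that links a participant's liver results across visits.

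**The concern.** The two AND rows are the only place in the summary tables where bilirubin and transaminase are tied to the same person. If the elevations peak at successive draws, the table shows one participant in a transaminase row and one in a bilirubin row, and nothing in it says whether that is one person or two. The combined rows show zero. A reader of the study report could take that zero to mean that no participant had both abnormalities, when the rule only establishes that no participant had both at one draw.

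Safety and tolerability is the primary objective, change in laboratory analytes is part of the secondary endpoint, and there is no control arm. With 11 and 22 participants planned, any joint liver signal would probably be a single case, so how that case is classified matters.

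**Working it through.** The documents state no figure for this rule, so there is none to reproduce. The check has three parts.

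**1. One constructed participant in Part B, run through the SAP rows.** Values are multiples of ULN, and ALP is 1 throughout.

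| | Day 14 | Day 28 | Day 42 |
|---|---|---|---|
| ALT | 6 | 2.5 | 1 |
| Total bilirubin | 1 | 2.5 | 1 |

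- ALT >3 and >5: yes (Day 14).
- ALT or AST >3 and >5: yes (Day 14).
- Bilirubin >1.5 and >2: yes (Day 28).
- Bilirubin >2 AND ALT or AST >3 at one timepoint: Day 14 fails on bilirubin, Day 28 fails on ALT (2.5 is not >3), Day 42 fails on both. **No.**
- The same with ALP >2: **No.**

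**2. All patterns over three post-baseline visits.** Score each visit as above or below the cut-off for ALT or AST (>3), bilirubin (>2) and ALP (>2). That gives 8 states per visit and 8^3 = 512 patterns.

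- Both transaminase and bilirubin above cut-off at some visit, not necessarily the same one: 512 x (7/8) x (7/8) = 392.
- Both above cut-off at the same visit: 512 x [1 - (3/4)^3] = 512 x 37/64 = 296.
- Omitted by the same-timepoint rule: 392 - 296 = 96. In all 96, both components still appear in the single-analyte rows.
- With ALP never above 2xULN: 49 patterns have both abnormalities and 37 have them together, so 12 are omitted.

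These are unweighted counts. They show that the gap exists and are not probabilities.

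**3. How often it might happen.** This needs durations and lags, which the documents do not give, so what follows is assumption. Let both elevations last L days, let bilirubin start d days after transaminase, and let visits fall every T days with onset at random between them. If L is at least T, each elevation is seen, and one visit sees both with probability min(1, (L - d)/T). The share left out is 1 minus that.

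| L (days) | T (days) | d = 3 | d = 7 | d = 10 |
|---|---|---|---|---|
| 14 | 14 | 1 - 11/14 = 21% | 1 - 7/14 = 50% | 1 - 4/14 = 71% |
| 21 | 14 | 18/14 exceeds 1: 0% | 14/14: 0% | 1 - 11/14 = 21% |
| 28 | 14 | 0% | 0% | 0% |
| 14 | 7 (Part A, Days 7-14) | 11/7 exceeds 1: 0% | 7/7: 0% | not computed |

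For L = 7 with T = 14 the formula does not apply. At d = 3, two visits 14 days apart cannot fall one in each elevation, so any pair that is seen is seen at one visit: 0% left out. At d = 10 the elevations do not overlap, so any pair that is seen falls at successive visits: 100% left out.

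The range is therefore 0% to 100% of cases in which both abnormalities were observed. The formula also treats visits as an unbroken regular grid, whereas each Part has only three scheduled post-baseline draws.

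**Scale.** One participant is 1/11 = 9.1% of Part A or 1/22 = 4.5% of Part B.

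**The case against.** The strongest answer is that nothing disappears from the report. The participant above is counted in the transaminase and bilirubin rows. Out-of-range values are flagged in the listings, and Listing 16.2.8.2 gives each participant's biochemistry. SAP 16.2 also sends any result judged clinically significant to the adverse event displays. With 11 and 22 participants, a reader can settle from the listing whether two counts are one person. These are descriptive counts; the primary endpoint, incidence of treatment-emergent adverse events, does not depend on them, and no test or stopping rule in the visible text does either. All of this stands and limits the weight of the point. It does not make the combined row say what a reader will take it to say.

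Two stronger readings are tempting. First, a reader might infer that most staggered cases would be missed, say 21% to 71%. Those figures come from fixing both durations at 14 days, equal to the Part B sampling interval; other assumptions give anything from 0% to 100%. Second, a reader might infer that the ALP row causes staggered cases to be missed or favours one type of injury. It does neither. The bilirubin-transaminase row has no ALP condition, so it counts every concurrent case whatever the ALP value, and a nested, stricter row beneath it is not an error. The omission comes from the timing rule alone.

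It can also be said that unscheduled and early termination results are already eligible under SAP 13.10. That is only partly an answer. Scheduled data take priority within a window, by-visit summaries use at most one record per participant, and the SAP does not say whether this selection applies to the liver rows counted over all post-baseline visits.

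**Conclusion.** The point holds as a limitation of the summary display. As written, a zero in the combined liver rows means that no participant crossed both cut-offs at the same timepoint. It does not mean that no participant crossed both during the study. The gap matters most in Part B, where draws are 14 days apart throughout, and across the Day 14 to Day 28 interval in Part A. Its frequency cannot be derived from the documents.

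This conclusion rests on the SAP text and needs no assumption about liver biology. It does not show that a case would go unseen, because the data remain in the listing and possibly in the adverse event tables. The weight is that of an inexpensive improvement to the reporting of a safety study. A separate row for cases with ALP not above 2xULN would be an optional refinement; its absence is not a fault in the plan.

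**What to change.** In SAP 16.2 and the matching table shells:

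1. Keep both same-timepoint rows and label them as such.
2. Add one row per Part that counts participants with maximum post-baseline ALT or AST >3xULN and maximum post-baseline total bilirubin >2xULN, regardless of visit. State that unscheduled and early termination results are included.
3. List the dated liver tests, including ALP, for every participant in either kind of row.

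The cost is a few sentences of SAP text, one table row per Part and one filtered listing, with no new data. The drawback is that the any-visit row may pair two unrelated abnormalities. The retained same-timepoint rows and the dated listing would show when that has happened.
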